There was one randomised controlled trial comparing annual to three-yearly screening in the UK. They found no statistically significant difference between the two arms in predicted survival using Nottingham Prognostic Index, but the confidence intervals were wide and it was underpowered.(19) There is limited evidence from observational studies examining different screening frequencies.

The previous extension of the upper age limit of screening from 64 to 70 is supported by women of these ages being included in some of the original RCTs of screening, although the balance of benefits and harms by age has mainly been assessed by economic modelling relying heavily on assumptions.(21) Screening has a higher cancer yield in older women, but

also increased risk of overdiagnosis.(21) In a recent survey of 21 countries, all of them screened up to at least age 70.(22) Recent advances in causal inference methods for observational data have been applied to examining the benefits and harms of colorectal cancer screening (20) but we believe we are the first group to propose to apply this approach to breast cancer screening.

4. Aims and Objectives

How does age of eligibility, screening interval and recall threshold affect the benefits and harms of breast cancer screening?

Aims:

1. To understand how age of eligibility, screening interval, and recall threshold for breast cancer screening affect benefits and harms including false positive recalls, overdiagnosis and mortality.
2. To inform revision of the quality assurance guidelines for breast screening centres based on maximising benefit and minimising harm from breast screening

Work Package 1: Database development and access

Objective 1: To assemble, clean and assess the quality of the combined datasets

- a. To obtain approvals to re-use the observational dataset of 13 million women offered breast screening
- b. To clean data and describe quality

Work Package 2: Causal links between age of eligibility, screening interval, recall threshold and health outcomes

Objective 2: To analyse the causal effect of age of eligibility, screening interval, and recall threshold on intermediate outcomes (numbers of breast cancers detected at screening by cancer type, interval cancers, false positive recalls) and health outcomes (mortality, morbidity, overdiagnosis).

Work Package 3: Pathway to impact

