grade 1/2/3, DCIS grade 1/2/3, DCIS surgical size (mm), Invasive surgical size (mm), invasive cancer type, hormonal status, Nottingham Prognostic Index].

5. Morbidity. Here we are interested in the morbidity associated with breast cancer treatment. We measure this as four outcomes: women receiving breast surgery, axillary surgery, radiotherapy, and chemotherapy within one year of diagnosis. Each of these are binary outcomes for each episode of cancer for each woman.
6. False positive recalls. These are women recalled from screening for extra tests but those extra tests do not indicate cancer. These data are taken from the NBSS computer system which automatically records who is recalled. This is measured as any women who were recalled but did not have cancer detected in follow up tests. It is a binary outcome for each episode of screening for each woman. This is an important harm of screening because it is associated with increased anxiety in women screened.

We will investigate the mechanism of action linking the three exposures to the outcomes. In particular we will investigate the relationship between characteristics of cancer detected, and women's outcomes such as overdiagnosis and mortality and morbidity associated with treatment. This analysis has dual purposes: firstly when inferring causation from observational research, in addition to appropriate accounting for confounding, it is important to elucidate the mechanism of action. Secondly, it is an important research output in its own right, to provide the evidence base for policy-makers to link the characteristics of cancers detected to benefits and harms of screening, when assessing a range of changes to screening. In the UK and Australia this is referred to as the linked evidence approach, and the US Preventative Services Task Force refer to it as the dotted line in the analytic framework.

How do two extra invitations to screening between the ages of 65 and <71 years affect all-cause and breast cancer specific mortality, overdiagnosis, treatment associated morbidity, and false positive recalls, in women already invited to screening age 50-64? (analysis led by [name], carried out at Bristol)

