How does screening intervals of between 15 and 27 months, compared with intervals of between 28 and 40 months affect cancer stage at diagnosis, treatment associated morbidity, and false positive recalls in women attending breast cancer screening age 50-70 years? (analysis led by [name], carried out at Bristol)

We will use the 'clone, censor and weight' approach described by Hernán.(25) Women will be eligible if screened between ages 50-70 years, and follow-up will start 15 months after the date of first invitation to screening. Follow-up for each woman will be duplicated ('cloned'), with one copy assigned to each treatment strategy. Follow-up for each cloned copy will be until women deviate from the strategy assigned that copy, because they are invited to screening too late (in the more frequent screening group) or too early (in the less frequent screening group). We will model the probability of being screened over time, in order to derive inverse-probability of screening weights. Moving house (and screening centre) will be included as a covariate, as this can prompt a shorter screening interval. These weights will be used to adjust for the selection bias introduced by censoring follow-up at the time of deviation from assigned treatment strategy. Planned shorter screening intervals due to suspicious findings at baseline will be excluded.

Additional analyses of will be conducted to investigate whether the effects of screening interval on health outcomes vary according to age group at screening (50-60 or 61-70 years).

Different definitions of round length will be investigated if time permits. This may include women attending family history screening and/or women whose round length was delayed by the COVID-19 pandemic.

How does recall threshold affect all-cause and breast cancer specific mortality, overdiagnosis, treatment associated morbidity, and false positive recalls in women attending breast cancer screening age 50-70 years? (analysis led by [name] and [name], undertaken at Birmingham and Warwick [[name] and [name] working across both universities])

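### Aim 1 and Objective 2 promise the effect of screening interval on mortality and overdiagnosis, but the interval question names neither, and its stage and treatment outcomes need per-woman reporting

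*Protocol*

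**What the plan says.** **What is promised.** Aim 1 covers three exposures (age of eligibility, screening interval, recall threshold) and how they "affect benefits and harms including false positive recalls, overdiagnosis and mortality". Objective 2 is "To analyse the causal effect of age of eligibility, screening interval, and recall threshold on intermediate outcomes" and on "health outcomes (mortality, morbidity, overdiagnosis". Neither makes an exception for interval. The Research Plan paragraph of the Summary of Research says the same about the frequency of invitation.

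**What is planned.** The age question asks how two extra invitations "affect all-cause and breast cancer specific mortality, overdiagnosis, treatment associated morbidity, and false positive recalls, in women already invited to screening age 50-64". The threshold question is "How does recall threshold affect all-cause and breast cancer specific mortality, overdiagnosis, treatment associated morbidity, and false positive recalls". The interval question compares 15 to 27 months with 28 to 40 months and asks how these "affect cancer stage at diagnosis, treatment associated morbidity, and false positive recalls in women attending breast cancer screening age 50-70 years". Further down, the interval text plans to examine "whether the effects of screening interval on health outcomes vary according to age group at screening (50-60 or 61-70 years", without listing the outcomes meant.

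**Related definitions (Measuring Outcomes).** The primary outcomes are headed as health outcomes or close proxies. They are, in order, breast cancer mortality, all-cause mortality, overdiagnosis, stage shift, morbidity and false positive recalls. Overdiagnosis is a difference in total cumulative incidence after enough follow-up, with a focus on 10 and 13 years. Morbidity is recorded as binary outcomes for each episode of cancer. No denominator is stated for stage shift.

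**The concern.** One exposure has two different outcome sets in the same document. Work Package 3 uses the results for possible changes in screening frequency, for reducing variability in intervals and for the round-length standard, and the Summary mentions flexibility in the interval target. A reader of Aim 1 would expect those recommendations to rest on a direct estimate of the effect on deaths and overdiagnosis. The interval question sets out no such estimate.

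The gap matters because the Background argues for going beyond proxy outcomes. The literature review notes that the UK randomised trial of annual against three-yearly screening used predicted survival and was underpowered.

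There is also a question of interpretation. More frequent screening can add early cancers to the count. If stage or treatment is summarised only among diagnosed cancers, the summary can look better although no advanced cancer has been prevented. The Protocol itself warns, for screen-detected cancer characteristics, that more detection may mean benefit or overdiagnosis.

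**Working it through.** **Step 1. Outcome lists side by side (primary outcomes 1 to 6).**

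| Primary outcome | Aim 1 | Objective 2 | Age question | Threshold question | Interval question |
|---|---|---|---|---|---|
| 1 Breast cancer mortality | yes (mortality) | yes (mortality) | yes | yes | no |
| 2 All-cause mortality | yes (mortality) | yes (mortality) | yes | yes | no |
| 3 Overdiagnosis | yes | yes | yes | yes | no |
| 4 Stage shift | not named | not named | not in the question | only in the 3-year model | yes |
| 5 Treatment morbidity | not named | yes | yes | yes | yes |
| 6 False positive recalls | yes | yes (as intermediate) | yes | yes | yes |

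Outcomes 1 to 3 are promised for interval and missing from its question. Both other questions include all three.

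**Step 2. Other routes to the missing outcomes.** The age-group sentence uses the label *health outcomes*, which in Measuring Outcomes covers mortality and overdiagnosis, so the interval text is unclear within itself. The mechanism analysis relates cancer characteristics to mortality and overdiagnosis for all three exposures. Neither passage sets out a direct comparison of the two interval strategies on these outcomes.

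**Step 3. Why the denominator matters (illustration only; these counts are not in the Protocol).** Take 100 cancers, 30 of them advanced, then add 10 early cancers that would otherwise never have been diagnosed, in the same number of women.
- Stage mix among cases: 30/100 = 30%, then 30/110 = 27.3%.
- Advanced cancers per woman: 30/N in both, unchanged.
- A treatment that none of the 10 receives: its per-cancer rate is multiplied by 100/110 = 0.91, and its per-woman rate is unchanged.
- A treatment that every case receives: 100/100, then 110/110, so the per-cancer rate stays at 100% while 10 more women are treated.

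Per-woman figures separate these situations and case-based figures do not.

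**Step 4. Could outcomes 1 to 3 simply be added to the same clones?** Follow-up starts 15 months after first invitation and runs until deviation from the assigned strategy. The windows end at 27 and 40 months, and no rule covers later rounds. The Protocol's focus for mortality and overdiagnosis is 10 and 13 years (120 and 156 months), and it states that short follow-up overestimates overdiagnosis. The same weighted data are therefore not clearly valid for these outcomes.

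**Step 5. Precision for mortality.** Table 1 gives 880,116 per group for 0.0443 against 0.0433 breast cancer deaths per 100 person-years (90% power, 5% level). The two-proportion formula with pooled variance gives 880,133 if those figures are entered as proportions (4.43% against 4.33%). Entered as rates, person-years per group = (1.960 + 1.282)² × (r1 + r2)/(r1 − r2)² = 10.507 × 0.000876/0.00001² ≈ 92 million. The whole dataset is described as having more than 100 million. Table 1 therefore cannot be cited as showing that a mortality comparison by interval is well powered.

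**The case against.** **The listed outcomes are themselves primary.** Stage shift, morbidity and false positive recalls are primary outcomes 4 to 6 and span benefit and harm. This stands: the interval question is not empty, and its estimates are useful in their own right.

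**The narrower list may be deliberate.** For threshold, the 3-year model is also limited to false positive recalls, interval cancers and stage. Longer horizons go to a final-round model, where follow-up is free of further invitations, or to a cumulative model if feasible. A short interval contrast among women still being invited fits that pattern. This is plausible, but the interval text does not say so, and interval has no longer-horizon companion model.

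**The stage denominator is not fixed.** Stage shift combines screen-detected and symptomatic cancers, and the design follows women over time, so a per-woman rate is possible. The denominator may be left to a statistical analysis plan that is not at hand. A reader might infer that the Protocol plans a misleading stage mix; the documents do not show that. What stands is narrower: morbidity is defined per episode of cancer, and total incidence is not listed for interval.

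**Two other stronger readings.** A reader might infer that mortality and overdiagnosis are plainly excluded for interval, or that the study can say nothing about them. The age-group sentence and the mechanism analysis rule out both: the text is unclear, and an indirect link is planned. A reader might also infer that the cure is to add these outcomes to the existing clones at little cost. Follow-up that stops at deviation, and the Protocol's own warning on short follow-up, do not support that.

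**Conclusion.** The contradiction is on the page and depends on no calculation. For screening interval, three of six primary outcomes are promised in Aim 1 and Objective 2 and absent from the interval question, without a reason, and the phrase used for the age-group analysis leaves their status open. As written, the direct interval comparison does not deliver the stated aim.

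The listed interval estimates are not invalid on this account. The need for per-woman reporting is a safeguard against one way of summarising stage and treatment. The 30% to 27% figure shows its direction under assumed counts and is not a forecast of bias in this study.

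**What to change.** 1. **Reconcile the passages, by one of two routes.**
   - Remove interval from the mortality and overdiagnosis parts of Aim 1, Objective 2 and the Research Plan paragraph. State why, limit the round-length and frequency claims in Work Package 3 to what the interval analysis estimates, and name the outcomes meant in the age-group sentence.
   - If the sponsor wants mortality and overdiagnosis for interval, specify a separate longer-horizon or sustained-strategy analysis with the 10- and 13-year focus and rules for later rounds. Present it as possibly imprecise, and do not rely on Table 1 for its power.
2. **In the interval analysis,** report advanced-stage cancers and each of the four treatments as cumulative incidence per woman followed, with total breast cancer incidence alongside. Proportions among diagnosed cases can be kept as a supplement. State that total incidence over this follow-up is not an estimate of overdiagnosis.

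Cost: the first route under item 1 is a text edit and leaves a narrower stated aim for interval. The second is a new analysis with its own design work. Item 2 is a little more analysis on the same weighted data.

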This proposed study would be an order of magnitude larger than the studies cited in the UK and US reviews, giving sufficient statistical power to investigate important outcomes for the woman screened, rather than proxies. We have individual patient data available, with very low rates of missing data and loss to follow-up as a result of the standardised software and mandatory reporting mechanisms in the English Breast Screening Programme.

There are previous UK studies which have investigated impacts of recall threshold. Blanks and colleagues investigated the relationship between needle biopsy rate (proportion of women screened who are recalled for further tests and one of those tests is a needle biopsy) and cancer detection rate. (16) They found a positive correlation, with diminishing returns at higher rates of biopsy. They did not present data on interval cancers or health outcomes. In a similar study Blanks and colleagues investigated the relationship between English and Dutch breast screening centres recall rates and cancer detection rates.(14) They concluded that increasing recall rates was associated with increasing detection rates of DCIS, although this relationship may have been subject to Country level confounding as Dutch recall rates were systematically lower. They did not present data on interval cancers. Burnside and colleagues found an inverse relationship between recall rate (a proxy for test threshold) and rate of interval cancers at UK breast screening centres, equivalent to one fewer interval cancer for every 80-84 recalls.(17) Duffy et al. found an inverse correlation between detection of DCIS and subsequent interval cancers. (18) All four of these studies were at the centre level rather than the individual or reader levels. Our proposed analysis uses data at the individual, reader and centre level so there are more units of analysis and we are able to adjust for individual or reader level variables. Further, this allows us to design the study explicitly considering whether we can make causal inference, whereas previous studies simply reported correlations. Finally, none of these previous studies extended analyses beyond cancer detection or interval cancer development, to longer term health outcomes, which we propose to do.

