Main data set (objective 1a): Our research team have already linked breast screening data from 80 English centres with English Cancer Registry and civil registration s mortality file data for 10 million women attending 35 million breast screening appointments, between 1988 and 2018 ([name], POSTBOx, NIHR, 572k). Data were extracted from centres up to 2018, but a date cut-off of date of first offered appointment up to end Dec 2016 was implemented in the previous data transfer to Warwick (for the previous POSTBOx project). The dataset for ATHENA-M will be based on this same database, but with the following additional data transferred to Warwick for analysis i. An additional 3 million women, who were offered screening but never attended, to enable intention to treat analysis ii. an additional outcome of cause of death, in particular breast cancer death. iii. Updated linkage to more recent follow-up in cancer registry to end 2018 and civil death registration to date of linkage in 2021. This transfer will be in two parts. Firstly, the expanded dataset with the extra 3 million women, without updating linkages or adding the extra outcome of cause of death. This first dataset will ensure there are data available in the event of issues arising in the reorganisation of Public Health England. The second transfer will contain updated linkages to the cancer registry (to end 2018/2019 as available) and civil death registration (to 2021), and extra outcomes of cause of death. Further updates to the database based on later extracts from NBSS (post 2016) and updated linkage to civil death registration, cancer registry and/or BSselect may be made to ensure these data are as current as possible. Summary of requested tables is in appendix 2, and full definition of all variables is in a separate document. Inclusion criteria is in appendix 3. This cohort definition gives 2.3 million women invited never screened between 1988 and 2016 when aged 47 to 73. These are additional to the 10.5 million women with at least one screened episode between 1988 and 2016 when aged 47 to 73.

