These data are more complete, and validated than any other breast screening data worldwide. They include >35 million screening appointments recalling >2.2 million women, detecting >250,000 cancers, with >100 million person-years of follow up to >500,000 subsequent deaths. Analyses are well powered, (sample size calculations are given in work package 2). There are little missing data, for example the radiologist's decision is missing in 4,527 (0.01% or 1 in 10,000) episodes, reader identifier is missing in 7,571 (0.02%) episodes. Many of these cases of missing data are from the early years of screening, between 1988 and 1993). Data are missing for the outcome of screening (cancer detected or not) in 6,992 (0.02%) episodes. Many of these are due to women dying between being recalled for further tests and attending for those tests, for these cases we have mortality data (which is the outcome in some analyses, and used for censoring in other analyses), so this may be an overestimation of data missingness.

The variables in the current dataset include:

- Details of each screening appointment (pseudonymised centre identifier, pseudonymised woman identifier, date (available for every appointment for each woman so screening interval is known), whether she attended, the decision of whether to recall and the pseudonymised identity of the first reader examining the mammograms, the decision of whether to recall and the pseudonymised identity of the second reader examining the mammograms, the decision and pseudonymised identity of the arbitrator of the decision whether to recall, whether she was recalled for further tests, whether she had a biopsy, whether she had cancer detected at screening (from biopsy results), whether this episode was part of a trial eg AgeX)

- Details of the woman (identifier to link to every screening episode she was invited to between 1988 and 2018, month and year of birth, index of multiple derivation from postcode)
- Details of screen detected cancers obtained through linkage to the English Cancer Registry (Histological grade, tumour node metastasis (TNM) stage, size, hormonal status (oestrogen receptor (ER),progesterone receptor (PR), human epidermal growth factor receptor 2 (HER2)), nodal involvement, treatment received (breast surgery, axillary surgery, radiotherapy, chemotherapy))

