1. Breast cancer mortality, as defined by the English Cancer Registry (where the initial source is the same but linkage to NBSS data more complete as uses multiple fields rather than just NHS number) checked against cause of death from the civil registrations mortality file. These sources have limited death data pre-1997, so we will also extract deaths data from NBSS to determine whether it can provide adequate quality, and if so use pre-1997. It is a binary outcome for each woman, with different lengths of follow up. Reported as cumulative incidence over all follow-up time, with focus on 10 year and 13 year to match previous systematic reviews.
2. All-cause mortality for everyone in the included cohort. This is taken from the civil registrations mortality file, which is populated by the Office of National Statistics. It is a binary outcome for each woman, with different lengths of follow up. Reported as cumulative incidence over all follow-up time, with focus on 10 year and 13 year to match breast cancer mortality.
3. Overdiagnosis. Overdiagnosis will be inferred as any difference between the study groups in total cumulative incidence of cancer (screen and symptomatic detected) after sufficient follow-up (the compensatory drop method). Therefore the outcome measured will be difference between groups in sum of breast cancers detected at screening and symptomatically. We will carefully consider length of follow-up in interpreting results relating to overdiagnosis, as insufficient follow up results in overestimation. We will publish a full protocol detailing all analysis methods and outcomes before commencing analysis to prevent selective reporting of outcomes or other analysis elements. Reported as cumulative incidence over all follow-up time, with focus on 10 year and 13 year to match breast cancer mortality.
4. Stage shift. This is defined by variables from the English Cancer Registry, including histological grade, cancer stage, and cancer size. The proposed mechanism of action of breast screening benefit is through detection of smaller earlier stage cancers. This will be measured for a combination of screen and symptomatic cancers, where differences between exposed and unexposed represents the stage shift of exposure. [In detail TNM stage (size, nodes, distant metastases), alternative nodal count to match Z11 and POSNOC trials 1/1-2/3+, DCIS vs invasive, invasive

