not accounted for in these calculation; however, we will adjust for these in the analyses where appropriate.

Table 1. Sample size requirements for detecting differences within the dataset. All calculations are for 90% power at 5% significance level. There are more than 30 million screening appointments in the dataset, from more than 10 million women.

Outcome	Baseline value	Change in value	Number required in each group to detect
Intermediate outcomes			
Recall rate	3.9%	0.1%	777,920
Cancer detection rate at screening	8.4/1000	0.5/1000	679,499
Small invasive cancer detection rate at screening	3.4/1000	0.3/1000	756,401
Interval cancer over 3 years	2.9/1000	0.3/1000	640,353
False positive recalls	3.1%	0.1%	641,114
Health outcomes			
All-cause mortality	0.6050 per 100 person-years	0.6025 per 100 person years	804,400
Breast Cancer mortality	0.0443 per 100 person years	0.0433 per 100 person years	880,116
Overdiagnosis	1.3% of women invited for screening for 20 years(1)	0.1%	279,869

We will deliver three journal articles, one for each of the three questions investigated: age of eligibility; recall threshold and round length. We will submit a fourth journal article exploring the link between detection of different cancer types and outcomes, with a focus on DCIS in particular. We will also present results to the UK National Screening Committee, and inform redrafting of the English national quality assurance standards for breast screening (see work package 3).

Work Package 3: Pathway to impact (Led by [name], PHE and [name], Warwick)

In addition to journal publication there are three strands to our dissemination strategy. 1. Influencing national policy directly via the UK National Screening Committee 2. Influencing national practice through national professional guidance and communication to health professionals 3. Communication to the public

1. Influencing national policy directly via the UK National Screening Committee (UKNSC)

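### Table 1 appears to enter the two mortality rates per 100 person-years as proportions; as rates, the stated differences need about 203 million (all-cause) and 92 million (breast cancer) person-years per group

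*Protocol*

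**What the plan says.** The caption of Table 1 states that "All calculations are for 90% power at 5% significance level". The last column gives a number required in each group, with no follow-up time attached, and the caption sets it against counts of appointments and women. The two mortality rows are:

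- All-cause: baseline "0.6050 per 100 person-years", changed value 0.6025, 804,400 per group.
- Breast cancer: baseline "0.0443 per 100 person years", changed value 0.0433, 880,116 per group.

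Work Package 1 (main data set) describes the data "with >100 million person-years of follow up to >500,000 subsequent deaths" and then says "Analyses are well powered, (sample size calculations are given in work package 2". The review of existing evidence claims a size "giving sufficient statistical power to investigate important outcomes for the woman screened, rather than proxies". Breast cancer mortality and all-cause mortality are the first and second primary outcomes. Breast cancer mortality is reported over all follow-up, "with focus on 10 year and 13 year to match previous systematic reviews", and all-cause mortality uses the same two horizons.

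**The concern.** A rate per 100 person-years and a proportion of women are different quantities, and a number of women cannot deliver a given power for a rate comparison unless follow-up is specified. At 0.605 deaths per 100 person-years, a difference of 0.0025 is a relative change of 0.4%. Detecting that with about 0.8 million women per group is implausible, because it needs millions of deaths.

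As printed, the table suggests that fewer than 2 million women in total suffice, out of more than 10 million, which is a wide margin. If that margin is not real, a null mortality result could later be read as evidence against a 0.4% or 2.3% relative difference when the study could not reliably detect one. The protocol intends the results to inform national screening policy and quality standards.

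**Working it through.** **Inputs.** From Table 1: the rates and numbers above, 90% power and 5% significance. Two-sided testing is inferred, because one-sided testing gives 655,608 and 717,333 for the mortality rows and matches neither. So z = 1.960 + 1.2816, and z² = 10.507. From Work Package 1: more than 100 million person-years, more than 500,000 deaths, and a cohort of 10.5 + 2.3 = 12.8 million women.

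**Step 1: reproduce the table.** Pooled two-proportion formula, equal groups, no continuity correction, with p̄ the mean of p₁ and p₂:

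n = [1.960·√(2p̄(1−p̄)) + 1.2816·√(p₁(1−p₁) + p₂(1−p₂))]² / (p₁−p₂)²

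| Row | Values entered | Formula | Stated |
|---|---|---|---|
| Recall rate | 3.9% vs 3.8% | 777,920 | 777,920 |
| Cancer detection | 8.4 vs 7.9 per 1000 | 679,498 | 679,499 |
| Small invasive cancer | 3.4 vs 3.1 per 1000 | 756,401 | 756,401 |
| Interval cancer | 2.9 vs 2.6 per 1000 | 640,352 | 640,353 |
| False positive recall | 3.1% vs 3.2% | 641,114 | 641,114 |
| Overdiagnosis | 1.3% vs 1.4% | 279,868 | 279,869 |
| All-cause mortality | 0.6050 vs 0.6025 as proportions | 804,399 | 804,400 |
| Breast cancer mortality | 0.0443 vs 0.0433 as proportions | 880,132 | 880,116 |

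The last row is 16 off (0.002%). The mortality figures are therefore consistent with comparing risks of 60.50% vs 60.25% and 4.43% vs 4.33%.

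**Step 2: is the unit label genuine?** 500,000 deaths / 100 million person-years = 0.5 per 100 person-years. So 0.6050 is an annual rate of about 0.6%, not a 60% risk.

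**Step 3: recompute as rates.** Person-years per group = 10.507 × (λ₁+λ₂) / (λ₁−λ₂)²

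- All-cause: 10.507 × 0.012075 / 0.000025² = 203.0 million per group, 406 million in total. Deaths: 203.0 million × 0.012075 ≈ 2.45 million.
- Breast cancer: 10.507 × 0.000876 / 0.00001² = 92.0 million per group, 184 million in total. Deaths: 92.0 million × 0.000876 ≈ 80,600.

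**Step 4: power of the printed numbers read as women.** Power = Φ[(λ₁−λ₂)/√((λ₁+λ₂)/T) − 1.960], where T is person-years per group, assuming constant rates and complete follow-up.

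| Follow-up | All-cause (804,400) | Breast cancer (880,116) |
|---|---|---|
| 10 years | 9% | 17% |
| 13 years | 11% | 21% |
| 27 years | 18% | 38% |

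At 10 years the shortfall is 203.0/8.044 ≈ 25-fold and 92.0/8.801 ≈ 10.5-fold.

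**Step 5: what the data could support.** An equal split of the stated 100 million person-years (T = 50 million) gives 36% and 67% power. The differences detectable at 90% power are then about 0.0050 per 100 person-years (0.8% relative) and 0.0014 (3% relative), against the table's 0.0025 (0.4%) and 0.0010 (2.3%).

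Upper bounds, assuming all 12.8 million women, complete follow-up and equal groups:

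- 10 years (T = 64 million): 44% and 77%.
- 13 years (T = 83.2 million): 55% and 87%.
- 27 years (T = 172.8 million): 85% for all-cause mortality.
- Mean follow-up needed for 90% power: 406/12.8 = 31.7 years for all-cause and 184.1/12.8 = 14.4 years for breast cancer mortality.

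**The case against.** **The table is only a feasibility check.** The protocol says that no formal calculation is required and that all eligible cases are used, so nothing in recruitment or analysis depends on these rows. That is true. But the section says the calculations are there to show that the data suffice, and the claim of good power refers the reader to them. For mortality they do not show it.

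**The differences chosen are very small.** Nothing in the protocol makes 0.4% or 2.3% the smallest effect that matters, and 100 million person-years equally split would detect about 0.8% and 3%. This stands: the error leaves the power claim for mortality unsupported by these rows, and does not show that larger effects would be missed. The comfort is limited, because no planned analysis is an equal split of the whole dataset.

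**The number might mean blocks of 100 person-years.** The breast cancer row would then be nearly right (880,116 against 920,450; 89% power). The table does not state that unit, and under it the all-cause row is still 2.5 times too small, with 53% power. One unit has to serve both rows.

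**The cause is inferred.** No formula is named, and the breast cancer match is not exact. This stands, but the printed numbers of women are inconsistent with the labelled rates whatever the cause.

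**The whole-cohort figures are hypothetical.** This also stands. The recall-threshold question concerns women who attend, so at most 10.5 million, which moves the breast cancer break-even to 184.1/10.5 = 17.5 years. The age-extension analysis uses only the 2000–2006 roll-out and women from 64 to under 71. The figures are upper bounds, and the planned analyses have less.

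**Conclusion.** The concern holds. Read as numbers of women, the two mortality entries in Table 1 do not give 90% power for the rates beside them. The stated differences need about 203 million and 92 million person-years per group.

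For all-cause mortality the stated difference is out of reach: 406 million person-years and 2.45 million deaths, against more than 100 million and more than 500,000 described. Even 27 years for every woman would give only 85%. For breast cancer mortality, the 184 million person-years needed exceed the stated figure, but that figure is a floor, so the shortfall cannot be fixed without the mean follow-up.

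These results assume two-sided 5% testing, equal groups, constant rates and no clustering; the protocol also ignores clustering in this table. The six other rows are unaffected. What is wrong is the stated precision for the first two primary outcomes, not the size of the cohort.

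**What to change.** - Recompute both mortality rows as comparisons of rates, and state the requirement in person-years or deaths: 203 and 92 million person-years per group if the present differences are kept.
- For the age-extension and recall-threshold analyses, the two with mortality outcomes, state the difference detectable at 90% power from the person-years each will really have. Treat recall threshold as a continuous exposure where appropriate; the two-group figures above are not that analysis's requirement.
- Qualify the statements on power in Work Package 1 and in the review of existing evidence so that they do not extend to mortality differences as small as those now in the table.

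The cost is one table and some wording, with no new data. The downside is that the figures for mortality become less favourable.
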